- 4). Weekly Assessments: At the end of the 5th and the 10th treatment and 1 week and 1 month follow-up visits, subjects will complete FTND, MNWS-R, Tobacco diary, mCEQ and adverse events.
- 5). At the end of the experiment, subjects will be asked what treatment (active or sham) he/she believes was completed.
- **9. Follow-up (Specific Aim 2).** The treatment period of the study will conclude on the end of two weeks. Participants will then enter the follow-up phase of the study. The two follow-up visits will be scheduled one 1 week and 1 month after the 10th rTMS session. Data will include craving ratings, tobacco diary, CO, QSU-B and FTND. We will conduct a follow-up phone survey of participants 3 months after the 10th treatment. Cigarette consumption will be evaluated by asking: 'How many cigarettes do you now smoke on an average day?'. Craving will be assessed by asking: 'How much do you want to smoke a cigarette right now on a scale from 1 to 10?' and "When was your last cigarette?'. Nicotine dependence will be assessed by the FTND.
- 10. Data Analyses. All data will be analyzed in consultation with Data Coordination Unit (DCU) at MUSC. Quantitative measures of nicotine dependence: Craving rating panel, Tobacco diary, CO, QSU-B and FTND. Side effects: Following standard procedures, frequency and severity measures of side effects will be constructed from the clinical measures. Significance testing: All tests will be two-sided, performed at significance α =0.05, except where noted. The statistical approach will use an ANOVA for each outcome variable. Some data may be longitudinal as well as cross-sectional and we will include random effects to account for within-subject correlation.

Power Analysis. The primary efficacy of rTMS for this study will be the abstinence rate and the number of cigarettes smoked per day at the end of treatment. One previous study of rTMS reported that 10 sessions of rTMS significantly reduced the number of cigarettes per day by the 10^{th} treatment ($18.11 \pm 2.61 \text{ vs.} 10.71 \pm 2.19$) ¹⁹. A power analysis was conducted based upon this two group design, a power of 0.8, and an alpha level of 0.05; a significant difference is anticipated with 18 subjects in each group. The attrition rate in the above mentioned study was 8%. The attrition rate for our previous study was 12% ³¹. According to the attrition

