rate from our study (which is more conservative), we will randomize 21 subjects per group (total N=42) to have ample power to detect a clinically meaningful difference. We will use 1 week, 1 month and 3 months follow-up data to calculate power for future R01 studies.

HUMAN SUBJECTS RESEARCH Protection of Human Subjects

- 1. Human Subjects Involvement and Characteristics. Subjects will be women and men aged 18 to 60 years. Subjects meeting inclusion/exclusion criteria (see detail in Study Plan) will be offered participation, regardless of racial/ethnic group. The sample composition will reflect the Charleston-area population distribution of healthy adult smokers.
- 2. Sources of Materials. Research material obtained from the individual subjects will include psychiatric examination results, drug (including nicotine) use assessment results, urine for cotinine levels, expired air breathalyzer alcohol and CO tests, blood samples, heart rate, skin conductance, and subjective ratings (e.g., craving). Urine samples for the urine drug screen and pregnancy will also be obtained. Research data will be obtained specifically for research purposes. We will not use existing specimens, records or data.
- 3. Potential Risks. Investigational Device Exemption: Transcranial Magnetic Stimulation is an investigational device. The IRB at MUSC (in cooperation with the FDA) has determined repetitive TMS to be a non-significant risk intervention.
 - 1). *Potential Risks of TMS:* The major risk using repetitive TMS subjects is the possibility of inducing a seizure. We have now studied and given rTMS to more than several hundred subjects over past 15 years. None of these patients has developed a seizure. We will exclude patients with a prior history of seizures. We have reported that single session doses of 12,960 stimulations were safely given to volunteers with inducing seizures ⁸⁵. We will carefully adjust each person's stimulus intensity to his or her motor threshold, before beginning treatment.
 - 2). Potential hearing loss: The discharge of the rTMS coil generates a high-energy click that may cause cochlear damage. Foam earplugs can protect against these changes and will be worn by the subjects and the researchers present during TMS sessions.
 - 3) Potential risks of active Sham TMS: When subjects receive sham TMS they may experience mild discomfort on their scalp.

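### The 18 per group does not follow from the cigarettes-per-day figures printed as its basis: read as SDs they give 3 per group, and the standardised difference of about 0.96 that 18 needs is not stated

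*Combined protocol and SAP*

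**What the plan says.** Section 10 (Data Analyses) of the combined protocol and SAP fixes the testing rule: "All tests will be two-sided, performed at significance α =0.05, except where noted". Its Power Analysis paragraph names the abstinence rate and cigarettes per day at the end of treatment as the primary efficacy measures, and then cites a single external result: "One previous study of rTMS reported that 10 sessions of rTMS significantly reduced the number of cigarettes per day by the" 10th treatment, with 18.11 ± 2.61 vs 10.71 ± 2.19 in brackets. It continues: "A power analysis was conducted based upon this two group design", with "a power of 0.8, and an alpha level of 0.05", and concludes that "a significant difference is anticipated with 18 subjects in each group".

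The 18 is then raised for 12% attrition: "we will randomize 21 subjects per group (total N=42) to have ample power to detect a clinically meaningful difference".

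The paragraph does not give an assumed SD, a standardised effect, a test or software. It does not say whether ± is an SD or a standard error, or which two things the means compare.

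**The concern.** A reader who enters the printed figures into a two-sample calculation does not get 18 or anything near it. Something other than those figures, or a particular unstated reading of them, must lie behind the stated size.

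This matters because it is the only sample-size justification in the document, and cigarettes per day is one of the two named primary efficacy measures. The paragraph ends by claiming ample power for a clinically meaningful difference, yet no such difference is defined. If the trial finds no difference, a reader who trusts that claim may take the result as evidence of no effect. The Research Plan says the findings will inform a larger, more definitive trial, so the misreading could carry forward.

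**Working it through.** **Inputs (Power Analysis paragraph, section 10).** Means 18.11 and 10.71; ± values 2.61 and 2.19; power 0.80; alpha 0.05 two-sided; two groups, 1:1; 18 per group before attrition; 12% attrition; 21 per group randomised. The test is not named, so a two-sample t-test with noncentral-t power is used.

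**Step 1: the part that reproduces.** 18 / (1 − 0.12) = 20.5, rounded up to 21. The attrition step is consistent.

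**Step 2: the 18, with ± read as SD.**
- Difference = 18.11 − 10.71 = 7.40.
- Pooled SD = √((2.61² + 2.19²)/2) = 2.409.
- Standardised difference d = 7.40 / 2.409 = 3.07.
- Power is 0.40 at 2 per group and 0.800 at 3 per group, so 3 per group are needed (2 by the normal approximation).

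No variant tried comes close to 18. One-sided testing, power of 0.90 or 0.95, or alpha of 0.025 or 0.01 gives at most 5 per group. A paired test gives 4 in total. At 18 per group and SD 2.41, power is above 0.999.

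**Step 3: what 18 per group corresponds to.** Solving for 80% power at n = 18 per group gives d = 0.961. If the difference is held at 7.40, SD = 7.40 / 0.961 = 7.70 (7.92 by the normal approximation). If the SD is held at 2.409, the difference is 0.961 × 2.409 = 2.3 cigarettes per day. Strictly, then, the missing input is d of about 0.96; the SD of 7.7 is one way to reach it.

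**Step 4: ± read as a standard error.** Then SD = 2.409 × √m, where m is the size of the source study's arms. The documents do not give m, so the values below are assumptions.

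| Assumed m | SD | n per group for 80% | Power at 18 per group |
|---|---|---|---|
| 8 | 6.8 | 15 | 0.89 |
| 10 | 7.6 | 18 | 0.81 |
| 12 | 8.3 | 21 | 0.73 |
| 15 | 9.3 | 26 | 0.64 |
| 20 | 10.8 | 35 | 0.52 |

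The stated 18 is recovered at m of about 10, and the answer moves quickly on either side of it.

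**Step 5: what the two means compare.** The sentence says rTMS reduced consumption and names no comparator, so it fits a before/after contrast in treated smokers as well as active against sham. If it is before/after, the active-minus-sham difference is 7.40 less any fall in the sham arm. With SD 7.7 and assumed sham falls (none is given in the documents):

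| Assumed sham fall (cigarettes/day) | Between-arm difference | Power at 18 per group |
|---|---|---|
| 1 | 6.4 | 0.68 |
| 2 | 5.4 | 0.53 |
| 3 | 4.4 | 0.38 |
| 4 | 3.4 | 0.25 |

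**Step 6: what the design can detect.** At 80% power, d = 0.96 with 18 completers per arm and 0.89 with 21. If the SD were 7.7, these are 0.961 × 7.7 = 7.4 and 0.886 × 7.7 = 6.8 cigarettes per day, or 41% and 38% of 18.11.

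**The case against.** The strongest reply is that 18 may be perfectly sound and merely under-explained. If ± denotes standard errors from arms of about 10, the calculation returns exactly 18. It could also have come from a deliberately cautious target, such as 2.3 cigarettes per day at SD 2.41, or from an SD taken from another source. The text does not say which difference or SD was entered, so it cannot be asserted that 7.40 was used as a between-arm difference. This stands, and it is why the point is about traceability.

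A reader might infer from the tables that the trial is underpowered. The documents do not support that. Read as SDs, the printed figures make the trial heavily overpowered for a difference of 7.40. Read as standard errors from arms of 8 or 10, they meet the 0.8 target. The shortfalls appear only under assumed source arms of 12 or more, or assumed sham falls combined with an assumed SD. They also take 18 completers; with all 21 per arm observed, the m = 12 case reaches 0.80. And they use a plain t-test, whereas section 10 allows random effects for longitudinal data.

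It can also be said that this is an exploratory R21, meant partly to supply data for powering later work. That lowers the stakes. It does not excuse a claim of ample power that the printed inputs cannot support.

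**Conclusion.** The concern holds as a failure to reproduce, and it should be fixed. On the only reading that uses the printed figures as they stand (mean ± SD), the answer is 3 per group against a stated 18. Getting to 18 takes a standardised difference of about 0.96, which is printed nowhere, or a standard-error reading with a source arm size that is not given. The plausible readings run from power above 0.999 to about one half at 18 per group, and lower still if the contrast is before/after with a sizeable sham fall. The 0.8 and the ample-power claim therefore have no support a reader can check.

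Two stronger conclusions are tempting and should not be drawn: that the trial is too small, and that standard errors are the only route to 18. The first rests on arm sizes and sham falls that are assumed here. The second is contradicted by the alternative in Step 3. The results rest on a two-sample t-test at two-sided alpha 0.05 with equal arms.

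**What to change.** Keep N=42 and rewrite the Power Analysis paragraph so that it:
- states the assumed active-minus-sham difference in cigarettes per day, the SD with its source, and the test used;
- labels the ± values as SD or standard error (with the source arm sizes if the latter), and says whether 18.11 and 10.71 are two arms or two time points;
- replaces the ample-power wording with the detectable difference: 0.96 SD with 18 completers per arm, 0.89 SD with 21;
- shows power over a range of SDs. For a difference of 7.40 at 18 per group, for example: SD 6, 0.95; SD 7, 0.87; SD 8, 0.77; SD 9, 0.67; SD 10, 0.58. If the cited means prove to be before/after, show power for smaller between-arm differences as well.

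The cost is one rewritten paragraph and a short table. There are no extra participants and no change to endpoints or procedures. The stated power may look less favourable once the SD and contrast are made explicit.

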seizure by prescreening subjects for a seizure history, getting a detailed medication history and by tailoring each person's TMS intensity to their own motor (and indirectly seizure) threshold. We will exclude subjects if they are taking medications that are associated with lowering of seizure threshold including stimulants (except for caffeine). We will minimize hearing damage by having all subjects wear earplugs to protect their hearing during the TMS sessions. Subjects will be stimulated with TMS in private clinical settings. A resuscitation cart including an Ambu bag and oxygen will be available. A licensed MD will be readily available during all TMS procedures to quickly respond to medical emergencies if they should arise.

5. Potential Benefits Of The Proposed Research To The Subjects And Others

For the proposed studies, the risks are minimal with very little chance of long-term or serious harm. Participants may experience a reduction in the number of cigarettes smoked per day and cigarette craving as benefit from study participation. Subjects will be compensated \$70 for the screening visit which includes \$20 for drug screen, \$25 for physical examination and assessments, and \$25 for the baseline MRI. Subjects will be compensated \$40 per visit for each visit attended during the treatment. Subjects will be compensated \$25 for MRI scanning. During the follow-up phase of the study, subjects will be compensated \$50 at the 1 week and 1 month visits. Thus, the total compensation could potentially equal \$595 over 3 months, depending on the number of visits. Subjects will be paid in cash.

Payments subjects receive from MUSC for participating in a research study are considered taxable income per IRS regulations. Payment types may include, but are not limited to: checks, cash, gift, certificates/cards, personal property, and other items of value. If the total amount of payment you receive from MUSC reaches or exceeds \$600.00 in a calendar year, you will be issued a form 1099.

6. Subject Safety And Minimizing Risks (Data And Safety Monitoring Plan)

- 1). *Trial Management:* The study will be managed from the Brain Stimulation Lab within the Department of Psychiatry and Behavioral Sciences at the Medical University of South Carolina.
- 2). Data Management and Analysis: Data will be entered by research assistants directly into a computer using standard database software. The data analysis plan is outlined in the Data Analysis Plan section.
- 3). Quality Assurance: The PI will have weekly meetings with the research assistants to discuss qualitative comments received during data collection and any problems in data collection. The statistician will periodically examine the database to look for irregularities. Initial data analyses will examine distributions of variable scores, and comparability of baseline characteristics across conditions in case analyses need to be adjusted for these. Confidentiality protections are outlined above.
- 4). Regulatory Issues: All unexpected Adverse Events (AEs) will be reported to the MUSC IRB and Committee on Human Research within 48-business hours. Serious AEs will be reported within 24-business hours. Follow-up of all unexpected and serious AEs will also be reported to these agencies.
- 5). Definition of AE and SAE: An AE is defined as any untoward medical occurrence in a study subject administered a pharmaceutical product that does not necessarily have a causal relationship with this treatment (ICH GCP). Any unwanted change, physically, psychologically or behaviorally, that occurs in a study participant during the course of the trial is an adverse event. A Serious Adverse Event (SAE) is defined as an adverse event that has one of the following outcomes: death, life-threatening, inpatient hospitalization or prolongation of existing hospitalization, persistent or significant disability/incapacity, a congenital anomaly/birth defect.
- 6). Documentation and Reporting: AEs/SAEs are documented and reported as per IRB requirements. Research staff will identify adverse events and obtain all available information to assess severity, seriousness, study relatedness, expectedness, outcome and the need for change or discontinuation in the study intervention. Adverse events are generally documented on AE Logs and AE Case Report Forms (CRFs). Additional relevant AE information if available will be documented in a progress note in the research record as appropriate to allow monitoring and evaluating of the AE. If the AE meets the definition for serious, appropriate SAE protocol specific reporting forms are completed and disseminated to the appropriate persons and within the designated timeframes as indicated above. For each AE/SAE recorded, the research staff will follow the AE/SAE until resolution, stabilization or until the participant is no longer in

the study as stated in the protocol. We will report adverse events to the Medical MUSC IRB online per the IRB's guidelines.

7). Inclusion of Women and Minorities: Both men and women who meet study criteria will be eligible to participate. Since this study is designed to examine adult smokers, children will not be included. Our minority enrollment is limited by the demographics of our county and state. At MUSC, the population of our county (Charleston, South Carolina) includes 0.3% Native American, 1.1% Asian American, 34.5% African-American, 0.1% Native Hawaiian or other Pacific Islander, and 2.4% Hispanic. We anticipate a recruitment and participation of minorities lower than what the Census 2000 reports for Charleston County since a large portion of Charleston County is rural and suffers from similar 'barriers for mental health treatment' identified by the Surgeon General's 2001 report and African Americans smoke at lower rates than Caucasians. In addition, MUSC is centrally located and in proximity of both major African-American and Hispanic communities in Charleston. We will take advantage of several intensive out-reach programs already in place at MUSC to enhance minority recruitment. For the reasons listed above we expect our enrollment to include 2% of Hispanics, 15% African-Americans or Blacks and 1.4% of Asians. Other minorities are almost non-existent in our catchments area.

Targeted/Planned Enrollment: Number of Subjects						
	Sex/Gender					
Ethnic Category	Females	Male	Total			
Hispanic or Latino	1	1	2			
Not Hispanic or Latino	20	20	40			
Ethnic Category Total of All Subjects*	21	21	42			
Racial Categories						
American Indian/Alaska Native	0	0	0			
Asian	0	0	0			
Native Hawaiian or Other Pacific Islander	0	0	0			
Black or African American	3	3	6			
White	18	18	36			
Racial Categories: Total of All Subjects*	21	21	42			

F. REFERENCES/LITERATURE

- 1. Smoking-attributable mortality, years of potential life lost, and productivity losses--United States, 2000-2004. *MMWR Morb Mortal Wkly Rep.* Nov 14 2008;57(45):1226-1228.
- 2. Quitting smoking among adults--United States, 2001-2010. MMWR Morb Mortal Wkly Rep. Nov 11 2011;60(44):1513-1519.
- 3. Hughes JR. Effects of abstinence from tobacco: valid symptoms and time course. *Nicotine Tob Res*. Mar 2007;9(3):315-327.
- **4.** Hughes JR. Measurement of the effects of abstinence from tobacco: a qualitative review. *Psychol Addict Behav.* Jun 2007;21(2):127-137.
